## VERSION CONTROL

---

Version	Date	Author	Description of Changes
Final 1.0	16-Jan-2022	[REDACTED]	Not applicable

## ABBREVIATIONS

---

AE	Adverse Event
ALT	Alanine Aminotransferase
ARCI	Addiction Research Center Inventory
AST	Aspartate Aminotransferase
AUC 0-inf	Area under the concentration-time curve from the time 0 extrapolated to infinity
AUC 0-t	Area under the concentration-time curve from time 0 to t h
AUC 0-T	Area under the concentration-time curve from time 0 to the last measurable observed concentration
BMI	Body Mass Index
BUN	Blood Urea Nitrogen
C	Positive Control
CFB min	Change from baseline to minimum effect (predose - postdose)
CI	Confidence Interval
C max	Maximum observed concentration
CRU	Clinical Research Unit
CSR	Clinical Study Report
C-SSRS	Columbia-Suicide Severity Rating Scale
CV%	Coefficient Of Variation Percentage
DMP	Data Management Plan
DTS	Deviation Tracking System
ECG	Electrocardiogram
eCRF	Electronic Case Report Form
E max	Maximum effect
E min	Minimum effect
ER	Extended Release
EtCO 2	End Tidal CO 2
FSH	Follicle Stimulating Hormone
HAP	Human Abuse Potential
HBsAg (B)	Hepatitis B Virus Surface Antigen
HCV (C)	Hepatitis C Virus Antibody
HEENT	Head, Eyes, Ears, Nose, Throat
HIV	Human Immunodeficiency Virus
ICF	Informed Consent Form
ICH	International Conference on Harmonisation
λ Z	Individual estimate of the terminal elimination rate constant, calculated using log-linear regression of the terminal portions of the plasma concentration-versus-time curves

LLOQ	Lower Limit of Quantitation
ln	Natural Log
Max	Maximum
MBG	Morphine-Benzedrine Group
MCV	Mean Corpuscular Volume
MedDRA	Medical Dictionary For Regulatory Activities
Min	Minimum
MOAA/S	Modified Observer's Assessment of Alertness/Sedation
n	Number of Subjects
N	Number of Observations
NCA	Non-Compartmental Analyses
P	Placebo
PCAG	Pentobarbital-Chlorpromazine-Alcohol Group
PD	Pharmacodynamic(s)
PK	Pharmacokinetic(s)
PT	Preferred Term
Q1	First Quartile
Q3	Third Quartile
SAE	Serious Adverse Event
SAP	Statistical Analysis Plan
SD	Standard Deviation
SE	Standard Error
SOC	System Organ Class
SOP	Standard Operating Procedure
SpO 2	Oxygen Saturation
SUSAR	Suspected Unexpected Serious Adverse Event
T	Test Drug
T 1/2	Terminal elimination half-life
T last	Time of the last measurable observed concentration
T max	Time of maximum observed concentration
TA_AOE	Time-averaged area over the effect-time curve
TA_AUE	Time-averaged area under the effect-time curve
TEAE	Treatment-Emergent Adverse Event
TE max	Time of maximum effect
TE min	Time of minimum effect
TFLs	Tables, Figures, and Listings
UDS	Urine Drug Screen
VAS	Visual Analog Scale
VC	Variance Components
WHO-DDE	World Health Organization Drug Dictionary - Enhanced

## 1. INTRODUCTION

---

This study will be a randomized, double-blind, active- and placebo-controlled, 5-way crossover study to determine the abuse potential of GE-IR relative to alprazolam and placebo, in healthy, nondependent, recreational drug users with sedative drug use experience. This study will consist of 3 phases: screening, qualification and treatment.

This statistical analysis plan (SAP) provides a detailed description of the statistical methods and procedures to be implemented for the analyses of data from protocol AR26.3031.1. Pre-planning of analyses reduces the potential for bias and often reduces disputes between sponsor and the regulatory authority regarding the validity of the results. The same principles apply to supportive and/or post-hoc analyses. These analyses must be prospectively specified. (Good Review Practice: Clinical Review of Investigational New Drug Applications, December 2013).

The analyses described in the SAP are based upon the final protocol version 3.0 (Amendment 02), dated 09-Aug-2021.

## 2. STUDY OBJECTIVES

Horizant® is formulated as an extended release (ER) formulation of gabapentin enacarbil. The primary purpose of this study is to evaluate the abuse potential of gabapentin enacarbil immediate-release (GE-IR), the active moiety in Horizant in comparison to placebo and an active control with known abuse potential (i.e., alprazolam).

The objectives of the study and corresponding study endpoints are detailed in Table 1.

Table 1: Objectives and Related Endpoints

Objective(s)	Endpoint	Analysis
Pharmacodynamic (PD)		
To evaluate the abuse potential of single oral doses of GE-IR relative to alprazolam and placebo, when administered to nondependent recreational drug users with sedative drug use experience	
The primary endpoint will be the maximum (peak) effect (<math>E_{max}</math>) over 24 hours for Drug Liking (“at this moment”), assessed on a bipolar (0 to 100 points) visual analog scale (VAS).
 
Key Secondary PD endpoints will be:
 
 
• Overall Drug Liking VAS (<math>E_{max}</math>)
 
• Take Drug Again VAS (<math>E_{max}</math>)
 
• High VAS (<math>E_{max}</math>)
 
 
Non-Key Secondary PD endpoints will be:
 
Balance of Effects
 
 
• Drug Liking VAS (time of maximum effect [<math>TE_{max}</math>], minimum effect [<math>E_{min}</math>], time of minimum effect [<math>TE_{min}</math>], and time-averaged area under the effect-time curve [TA_AUE])
 
 
Positive Effects
 
 
• Good Effects VAS (<math>E_{max}</math>, <math>TE_{max}</math>, and TA_AUE)
 
• High VAS (<math>TE_{max}</math>, and TA_AUE)
 
 
Negative Effects
 
 
• Bad Effects VAS (<math>E_{max}</math>, <math>TE_{max}</math>, and TA_AUE)
 
 
Other Subjective Effects
 
 
• Any Effects VAS (<math>E_{max}</math>, <math>TE_{max}</math>, and TA_AUE)
 
• Feeling Drunk VAS (<math>E_{max}</math>, <math>TE_{max}</math>, and TA_AUE)
 
• Drowsiness/Alertness VAS (<math>E_{min}</math>, <math>TE_{min}</math>, and time-averaged area over the effect-time curve [TA_AOE])
 
• Relaxation/Agitation VAS (<math>E_{min}</math>, <math>TE_{min}</math>, and TA_AOE)
 
• Addiction Research Center Inventory
 
	Refer to Section 7.4.1

Objective(s)	Endpoint	Analysis
	
(ARCI) Morphine-Benzedrine Group (MBG) Scale (<math>E_{max}</math>, <math>TE_{max}</math>, and <math>TA\_AUE</math>)
 
 
• ARCI Pentobarbital-Chlorpromazine-Alcohol Group (PCAG) Scale (<math>E_{max}</math>, <math>TE_{max}</math>, and <math>TA\_AUE</math>)
 
 
Observer Assessments
 
 
• Modified Observer's Assessment of Alertness/Sedation (MOAA/S) (<math>E_{min}</math>, change from baseline to minimum effect [<math>CFB_{min}</math>], and <math>TA\_AOE</math>)
 
	
Pharmacokinetic (PK)		
To evaluate the PK of GE-IR when administered to nondependent, recreational drug users with sedative drug use experience	Secondary Endpoint: Pharmacokinetic parameters of GE-IR include $C_{max}$ , $T_{max}$ , $T_{last}$ and area under the concentration-time curve from 0 to the last measured observable concentration ( $AUC_{0-T}$ )	Refer to Section 8
Safety		
To evaluate the effects on safety and tolerability of single oral doses of GE-IR relative to alprazolam and placebo, when administered to nondependent, recreational drug users with sedative drug use experience	Secondary endpoints will include a summary of the incidence of adverse events (AEs), serious adverse events (SAEs), as well as descriptive summary and statistics of the safety parameters which include clinical laboratory values, vital signs (i.e., systolic and diastolic blood pressure, pulse rate, respiratory rate, oral temperature, oxygen saturation [ $SpO_2$ ]), continuous $SpO_2$ monitoring, continuous End Tidal $CO_2$ , electrocardiograms [ECGs], Columbia Suicide Severity Rating Scale (C-SSRS), and physical examination findings.	Refer to Section 9

## 3. STUDY DESIGN

---

### 3.1 Overall Study Design

This study will be a randomized, double-blind, active- and placebo-controlled, 5-way crossover study to assess the abuse potential, safety, and PK of GE-IR relative to alprazolam and placebo, in healthy, nondependent, recreational drug users with sedative drug use experience.

This study will consist of 3 phases: screening, qualification and treatment. The study schema is presented in Figure 1.

After a screening period of up to 30 days, eligible subjects will be admitted to the clinical research unit (CRU) and randomized (1:1) into the double-blind qualification phase. During the qualification phase, subjects will receive oral doses of alprazolam 2 mg (active control) and matching placebo in a randomized, double-blind, crossover manner to ensure they are able to discriminate and show positive effects of the active control in a clinical setting and to demonstrate that they are able to tolerate the administered dose. Two doses in the qualification phase will be separated by 48 hours.

Subjects will be encouraged to remain in the CRU but may be discharged between the qualification phase and treatment phase, if necessary. A minimum 3-day washout will be required between the last dose in the qualification phase and the first dose of the treatment phase. Appropriate discharge and re-admission procedures are noted in Appendix A.

[figure not shown]
The treatment phase is a randomized, double-blind, active- and placebo-controlled 5-way crossover design. Subjects will be randomized to 1 of the 10 pre-specified treatment sequences in which they will receive the following 5 treatments in a crossover manner (1 per treatment period) in blinded fashion:

- Placebo
- Alprazolam 2 mg (active control)
- GE-IR 200 mg
- GE-IR 450 mg
- GE-IR 700 mg

Each study drug administration will be separated by at least 3 days. Drug administration will occur on the first day of each treatment period followed by PD, PK, and safety assessments for up to 24 hours postdose. Subjects will be discharged from the investigational site approximately 24 hours after the final dose if deemed medically stable for discharge by an investigator.

The maximum duration of subject participation will be approximately 49 days, including screening.

Figure 1: Study Schema

Note: the sequence of treatments shown is for illustration of the overall design and does not necessarily represent an actual treatment sequence. Refer to Table 2 and Table 3 for all treatment sequences. A minimum 3 day washout will be required between the last dose in the qualification phase and the first dose of the treatment phase.

### 3.3 Determination of Sample Size

As reported in an unpublished human abuse potential (HAP) study evaluating doses of 1.5 mg and 3.0 mg of alprazolam, the mean paired difference (SD) for Drug Liking VAS  $E_{max}$  VAS between alprazolam 1.5 mg and placebo was 26.3 (18.62). For alprazolam 3.0 mg vs. placebo, the mean difference (SD) was 26.6 (17.83). A margin of 15, with a correlation of 0, and an upper-tailed test with a significance level of 0.05 results in 48 completers for the comparison of alprazolam 1.5 mg vs. placebo, and 42 completers for the comparison alprazolam 3.0 mg vs. placebo. The more conservative sample size estimate of 48 subjects will be used.

Assuming a drop-out rate of approximately 25%, and allowing for missed data and problematic subjects as defined for the Modified Completer population, approximately 60 subjects are planned for randomization into the treatment phase in order to achieve a minimum of 48 completers (at least 4 subjects per 10 treatment sequences).

Due to potential sedative effects that may prevent subjects from completing measures and expected natural attrition, replacement subjects may be considered in order to meet the minimum number of completers, in the event that the preplanned attrition rate of 25% is surpassed.

Subjects will be consecutively randomized into the qualification phase until the target number of 60 subjects eligible for participation in the treatment phase is reached.

### 3.4 Treatments

The following treatments will be administered with approximately 240 mL of room temperature water in the morning under fasted conditions during the qualification phase:

- **Placebo:** A single dose of placebo to match alprazolam (2 lactose 100 mg tablets over-encapsulated in one Swedish Orange Opaque AAEL-DB capsule) will be administered orally.
- **Active Control:** A single 2 mg dose of alprazolam (2 × 1 mg tablets over-encapsulated in one Swedish Orange Opaque AAEL-DB capsule) will be administered orally.

The following treatments will be administered with approximately 240 mL of room temperature water in the morning under fasted conditions during the treatment phase:

- **Placebo:** Three placebo capsules to match GE-IR + 1 placebo capsule to match alprazolam [2 × over-encapsulated placebo tablets in one size 0 opaque white capsules with no markings] will be administered orally.
- **Active Control:** A single 2 mg dose of over-encapsulated alprazolam (2 × 1 mg tablets over-encapsulated in one size 0 opaque white capsules with no markings) + 3 placebo capsules to match GE-IR will be administered orally.
- **A single 200 mg dose of GE-IR** (1 × 200 mg immediate-release [IR] capsule + 2 placebo capsules to match GE-IR capsule + 1 placebo capsule to match alprazolam [2 × 1 mg placebo tablets over-encapsulated in one size 0 opaque white capsules with no markings]) will be administered orally.
- **A single 450 mg dose of GE-IR** (2 × 225 mg immediate-release [IR] capsule + 1 placebo capsule to match GE-IR capsule + 1 placebo capsule to match alprazolam [2 × over-encapsulated placebo tablets in one size 0 opaque white capsules with no markings]) will be administered orally.
- **A single 700 mg dose of GE-IR** (3 × 233.3 mg immediate-release [IR] capsules + 1 placebo capsule to match alprazolam [2 × over-encapsulated placebo tablets in one size 0 opaque white capsules with no markings]) will be administered orally.

### 3.4 Study Procedures

For complete details on the study assessments to be performed for each study period, refer to Appendix A.

### 3.5 Randomization and Unblinding Procedures

#### 3.5.1 Method of Assigning Subjects to Treatment Groups

The designated, unblinded biostatistician will generate the separate randomization codes for the qualification and treatment phases with a computer program according to the study design, the number of subjects and the sequence of treatment administration. For the qualification and treatment phases, the random allocation of each sequence of treatment administration to each subject will be done in such a way that the study is balanced. Once generated, the randomization codes will be final and will not be modified.

Subjects who sign the informed consent form (ICF) and are randomized but do not receive a study treatment in the treatment phase may be replaced. Subjects who sign the ICF, are randomized and receive a study treatment in the treatment phase, and subsequently withdraw, or are withdrawn or discontinued from the study, may be replaced.

### 3.5.1.1 Qualification Phase

Subjects who enter the qualification phase will be assigned, in ascending order, a qualification randomization number to identify the sequence of their treatments Table 2.

Table 2: Sample Qualification Phase Sequences

Treatment Sequence	Day 1	Day 3
XY	X	Y
YX	Y	X

Treatment X: Placebo

Treatment Y: Alprazolam 2 mg

A minimum 3 day washout will be required between the last dose in the qualification phase and the first dose of the treatment phase.

### 3.5.1.2 Treatment Phase

For the treatment phase, qualified subjects will be randomized to 1 of 10 treatment sequences based on a computer-generated randomization schedule. The first dose will be administered at least 3 days after the qualification phase. The study drug will be prepared for each subject based on their randomization code. Subjects will receive all 5 treatments in the order specified by the treatment sequence according to two  $5 \times 5$  Williams square design (Table 3).

Table 3: Sample Treatment Phase Sequences

Treatment Sequence	Period 1	Period 2	Period 3	Period 4	Period 5
ABECD	A	B	E	C	D
BCADE	B	C	A	D	E
CDBEA	C	D	B	E	A
DECAB	D	E	C	A	B
EADBC	E	A	D	B	C
DCEBA	D	C	E	B	A
EDACB	E	D	A	C	B
AEBDC	A	E	B	D	C
BACED	B	A	C	E	D
CBDAE	C	B	D	A	E

Treatment A: Placebo

Treatment B: Alprazolam 2 mg

Treatment C: GE-IR 200 mg

Treatment D: GE-IR 450 mg

Treatment E: GE-IR 700 mg

### **3.5.2 Blinding**

The treatment assignment will not be known by the study subjects.

Furthermore, the randomization code will not be available to investigators and clinical staff involved in the collection, monitoring, revision, or evaluation of AEs, as well as clinical staff that could have an impact on the outcome of the study, including the biostatistician and pharmacokineticist (or delegate). When all PD assessments during the qualification phase have been completed for each cohort, the randomization will be released to allow for the evaluation of qualification criteria. For the treatment phase, the randomization will remain blinded until all the CRFs have been approved and signed.

The preparation and/or dispensing of the products will be performed by designated personnel that are not directly involved in the clinical aspects of the trial.

The randomization code must not be broken except in emergency situations where the identification of a subject's study treatment is required by an investigator for further treatment of the subject or by the designated unblinding person(s) in the case of a suspected, unexpected SAE (SUSAR) report. Randomization information will be held by designated individual(s). The date and reason for breaking the blind must be recorded.

## 4. ANALYSIS POPULATIONS

---

### 4.1 Qualification Phase

#### 4.1.1 Qualification Randomized Population

The Qualification Randomized population will include all subjects who are assigned a randomization number in the qualification phase.

#### 4.1.2 Qualification Safety Population

The Qualification Safety population will include all subjects who are randomized into the Qualification phase and receive at least 1 dose of either the study drug or placebo.

### 4.2 Treatment Phase

#### 4.2.1 Randomized Population

The Randomized population will include all subjects who are assigned a randomization number in the treatment phase.

#### 4.2.2 Safety Population

The Safety population will include all subjects who are randomized into the treatment phase and receive at least 1 dose of 1 of the study drugs or placebo.

#### 4.2.3 Completer Population

All subjects in the Safety population who complete all 5 crossover periods in the treatment phase of the study, and have sufficient data for evaluation of the primary endpoint (based on a blinded review of data prior to database lock) will be included in the Completer population. Subjects who do not have at least 1 observation within 2 hours of  $T_{max}$  for each treatment for Drug Liking VAS will be excluded from the Completer population.

#### 4.2.4 Modified Completer Population

All subjects in the Completer population, excluding problematic subjects with unreliable responses which can alter study results, will be included in the Modified Completer population. For the Drug Liking VAS scale, the following elimination criteria will be used to define the Modified Completer population.

- a) Similar  $E_{max}$  scores (within a 5-point difference) for a subject across all study treatments (including placebo)

OR

- b)  $E_{max}$  for placebo > 60 AND the  $E_{max}(\text{placebo}) - E_{max}(\text{positive control}) \geq 5$

Criterion a) and b) will be applied to the Drug Liking VAS data on the Completer population. If no subjects are excluded when these criteria are applied, then the Modified Completer population is the same as the Completer population.

#### 4.2.5 Pharmacokinetic (PK) Population

All subjects in the Safety population who receive at least 1 dose of GE-IR, and have at least 1 PK concentration after dosing will be included in the PK population.

## **5. STUDY SUBJECTS**

---

### **5.1 Disposition**

#### **5.1.1 Qualification Phase**

All subjects who are randomized into the qualification phase will be entered into the database. Disposition tables and listings will be presented for all subjects in the qualification phase, and for qualification failures using the Qualification Randomized population.

#### **5.1.2 Treatment Phase**

Subject disposition will be summarized and listed for subjects randomized to the treatment phase using the Randomized population. Percentages will be calculated using the number of randomized subjects. Completion by population, by period, by study, and reasons for discontinuation will be included in this table.

Subject discontinuations will be summarized by last treatment prior to discontinuation during the treatment phase. Listings of subject disposition by completion/discontinuation will also be provided.

Subject exclusions from each population will be summarized and listed for each phase of the study. Randomization scheme and code will be listed for the each phase of the study.

### **5.2 Protocol Deviations**

All protocol deviations related to study inclusion or exclusion criteria, conduct of the study, subject management, or subject assessment (including PD and PK sample processing deviations) will be listed for the qualification and randomized phases using the Qualification and Randomized populations, respectively. Information for PD and PK sampling time deviations during the treatment phase will be derived programmatically, and presented in listings.

Deviations will be collected in the clinic deviation tracking system (DTS) and presented as entered in a general protocol deviation listing.

## **6. DEMOGRAPHIC AND OTHER BASELINE CHARACTERISTICS**

---

### **6.1 Qualification Phase**

Demographics, baseline characteristics and informed consent information will be listed for the Qualification Randomized population. Demographics and baseline characteristics (sex, age, race, ethnicity, body weight, height, BMI) will be summarized separately for the Qualification Randomized and Safety populations. Subjects who did not complete the qualification phase or were not randomized into the treatment phase will also be summarized.

### **6.2 Treatment Phase**

Demographics, baseline characteristics and informed consent information will be listed for the Qualification Randomized population. Demographics and baseline characteristics (sex, age, race, ethnicity, body weight, height, and body mass index (BMI)) will be summarized by each population in the treatment phase using descriptive statistics (number of subjects (n), mean, standard deviation (SD), minimum, median, and maximum for continuous variables, and number of subjects and the proportion of subjects for categorical variables).

Prior and concomitant medications will be assigned a 12-digit code using the most recent version of the World Health Organization drug code available. Prior and concomitant medications will be listed by subject for the Qualification Randomized population.

Histories of recreational drug use, alcohol use and smoking history will be summarized for the Randomized population using descriptive statistics and listed by subject for the Qualification Randomized population.

## 7. PHARMACODYNAMICS ANALYSIS

---

Unless otherwise specified, all available PD data and analysis results will be presented for the Modified Completer population.

### 7.1 Pharmacodynamics Assessments

Prior to completing the computerized pharmacodynamics measures, all subjects will undergo a scripted training and practice regimen with additional training sessions as necessary.

#### 7.1.1 Subjective Effects Visual Analogue Scales (VASs)

All VASs will be scored on a 100-point scale, as shown in Table 4. The VASs may be administered as bipolar or unipolar scales, as appropriate, and the choice is determined by the nature of the subjective effect being measured. When VASs are administered as bipolar scales, the neutral point equals 50 (e.g., Drug Liking, Overall Drug Liking, Take Drug Again, Drowsiness/Alertness and Relaxation/Agitation VAS). The neutral point will also be labeled with an anchor, such as “neither like or dislike.” When VASs are administered as unipolar scales, the anchors will be presented using text such as “Not at all” (score = 0) to “Extremely” (score = 100; e.g., Good, Bad, High, and Any Effects VASs). Scales that refer specifically to drug (e.g., Drug Liking, Good Effects VAS, Bad Effects VAS, and Any Effects VAS) are not administered at predose.

Table 4: Visual Analog Scale (VAS) Descriptions

Scale Interpretation	Include Predose	Type of Scale	Description	Question Text	Response Anchors
Balance	No	Bipolar	Drug Liking	At this moment, my liking for this drug is	0: Strong disliking 50: Neither like or dislike 100: Strong liking
Balance	No	Bipolar	Overall Drug Liking	Overall, my liking for this drug is	0: Definitely would not 50: Neither would or would not 100: Definitely would
Balance	No	Bipolar	Take Drug Again	I would take this drug again	0: Not at all 50: Neither would or would not 100: Extremely
Positive	Yes	Unipolar	High	At this moment, I am feeling high	
Positive	No	Unipolar	Good Effects	At this moment, I feel good drug effects	
Negative	No	Unipolar	Bad Effects	At this moment, I feel bad drug effects	

Scale Interpretation	Include Predose	Type of Scale	Description	Question Text	Response Anchors
Other	No	Unipolar	Any Effects	At this moment, I can feel any drug effect	
Other	Yes	Unipolar	Feeling Drunk	At this moment, I am feeling drunk	
Other	Yes	Bipolar	Drowsiness/Alertness	At this moment, my mental state is	0: Very drowsy 50: Neither drowsy nor alert 100: Very alert
Other	Yes	Bipolar	Relaxation/Agitation	At this moment, my mental state is	0: Very agitated 50: Neither agitated or relaxed 100: Very relaxed

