	
Other Subjective Effects
 
• Any Effects VAS (E_{max}, TE_{max}, and TA_AUE)• Feeling Drunk VAS (E_{max}, TE_{max}, and TA_AUE)• Drowsiness/Alertness VAS (E_{min}, TE_{min}, and time-averaged area over the effect-time curve [TA_AOE])• Relaxation/Agitation (E_{min}, TE_{min}, and TA_AOE)• Addiction Research Center Inventory (ARCI) Morphine-Benzedrine Group (MBG) Scale (E_{max}, TE_{max}, and TA_AUE)• ARCI Pentobarbital-Chlorpromazine-Alcohol Group (PCAG) Scale (E_{max}, TE_{max}, and TA_AUE) 
Observer Assessments
 
• Modified Observer's Assessment of Alertness/Sedation (MOAA/S) (E_{min}, CFB_{min}, and TA_AOE) 
Pharmacokinetic Endpoints: Pharmacokinetic parameters of GE-IR include maximum observed concentration (C_{max}), time of maximum observed concentration (T_{max}), time of last measurable observed concentration (T_{last}), and area under the curve from time 0 to the last measurable observed concentration (AUC_{0-T}).
 
Safety Endpoints: Endpoints will include a summary of the incidence of adverse events (AEs), serious adverse events (SAEs), as well as descriptive summary and statistics of the safety parameters. Safety parameters will include clinical laboratory values, vital signs (i.e., systolic and diastolic blood pressure, pulse rate, respiratory rate, oral temperature, oxygen saturation [SpO_2]), continuous SpO_2 monitoring, continuous End Tidal CO_2 monitoring, electrocardiograms (ECGs), Columbia Suicide Severity Rating Scale (C-SSRS), and physical examination findings.

Study Product, Dose, and Mode of Administration (proposed):	
Gabapentin Enacarbil Immediate Release (GE-IR) Capsules Manufacturer: Arbor Pharmaceuticals, LLC Mode of administration: Doses of GE-IR capsules including 200 mg (1×200 mg capsule), 450 mg (2×225 mg capsules) and 700 mg (3×233.3 mg capsules) will be administered orally according to the randomization schedule during the Treatment phase.

Active Control, Dose, and Mode of Administration:	
Over-encapsulated Xanax (alprazolam) 1 mg tablets Manufacturer: Pfizer, Inc. Mode of administration: Single doses of 2 mg alprazolam (2×1 mg tablets over-encapsulated in one Swedish Orange Opaque AAEL-DB capsule) will be administered orally according to the randomization schedule during the Qualification and Treatment phases.

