6.3.1 Subjective Effects

6.3.1.1 Visual Analogue Scales

All VASs will be scored on a 100-point scale, as shown in [Table 5](#). The VASs may be administered as bipolar or unipolar scales, as appropriate, and the choice is determined by the nature of the subjective effect being measured. Bipolar scales ask about the neutrality, the direction and the intensity of a subjective opinion, whereas unipolar scales only ask about the extremity or intensity of a subjective opinion. When VASs are administered as bipolar scales, a neutral point equal to 50 is embedded within the scale (e.g., Drug Liking, Overall Drug Liking, Take Drug Again, Drowsiness/Alertness VAS). The neutral point reflects a state whereby a subject is experiencing neither negative nor positive effects (e.g., neither dislike nor like the effects of the drug) and is labeled with an anchor, such as "neither like nor dislike." When VASs are administered as unipolar scales, anchors will be presented using text such as "Not at all" (score = 0) to "Extremely" (score = 100; e.g., Good, Bad, High, and Any Effects VASs). Unipolar scales do not include a neutral point but rather, a rating of "0" reflects the complete absence of a subjective effect while a rating of "100" reflects the maximum presence of a subjective effect (e.g., No Good Effects = 0, Extremely Good Effects = 100). Scales that refer specifically to drug (e.g., Drug Liking, Good Effects VAS, Bad Effects VAS, and Any Effects VAS) are not administered at predose.

Table 5. Visual Analog Scale (VAS) Descriptions

Scale Interpretation	Include Predose	Type of Scale	Description	Question Text	Response Anchors
Balance	No	Bipolar	Drug Liking	At this moment, my liking for this drug is	0: Strong disliked 50: Neither like nor dislike 100: Strong liked
Balance	No	Bipolar	Overall Drug Liking	Overall, my liking for this drug is	0: Definitely would not 50: Neither would nor would not 100: Definitely would
Balance	No	Bipolar	Take Drug Again	I would take this drug again	0: Definitely would not 50: Neither would nor would not 100: Definitely would
Positive	Yes	Unipolar	High	At this moment, I am feeling high	
Positive	No	Unipolar	Good Effects	At this moment, I feel good drug effects	
Negative	No	Unipolar	Bad Effects	At this moment, I feel bad drug effects	0: Not at all 100: Extremely
Other	No	Unipolar	Any Effects	At this moment, I feel any drug effect	
Other	Yes	Unipolar	Feeling Drunk	At this moment, I am feeling drunk	

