Other	Yes	Bipolar	Drowsiness/Alertness	At this moment, my mental state is	0: Very drowsy 50: Neither drowsy nor alert 100: Very alert
Other	Yes	Bipolar	Relaxation/Agitation	At this moment, my mental state is	0: Very relaxed 50: Neither relaxed nor agitated 100: Very agitated

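### SAP Table 4 reverses the protocol's Relaxation/Agitation VAS anchors without listing a change, while keeping endpoints that fit only the protocol's direction

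*SAP*

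**What the plan says.** Protocol section 6.3.1.1, Table 5, gives the anchors as "0: Very relaxed 50: Neither relaxed nor agitated 100: Very agitated". SAP section 7.1.1, Table 4, gives "0: Very agitated 50: Neither agitated or relaxed 100: Very relaxed".

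Each document makes its own table the scoring rule. The SAP states: "All VASs will be scored on a 100-point scale, as shown in Table 4". The protocol says the same of its Table 5.

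The endpoints are identical in the two documents. The protocol synopsis lists "Relaxation/Agitation (E_{min}, TE_{min}, and TA_AOE"), repeated in protocol section 2 and Table 7. SAP section 2, Table 1, lists "Relaxation/Agitation VAS ( E_{min} , TE_{min} , and TA_AOE"), among the non-key secondary endpoints.

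The SAP describes its analyses as "based upon the final protocol version 3.0 (Amendment 02), dated 09-Aug-2021". The legible entries in its section 12 concern PK parameters, the capsule description, demographic populations, added qualification-phase Emax summaries and the population for the AE listing. None concerns VAS anchors.

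**The concern.** The plan holds two opposite scoring rules for one scale, and the endpoints fit only one of them. With the relaxed end at 0, the minimum is peak relaxation, which is the effect of interest for a sedative comparator. With the agitated end at 0, the minimum is peak agitation. Peak relaxation would then be the maximum, which neither document plans to analyse for this scale.

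Two outcomes are possible. If the scores carry the protocol coding, the derived values are correct, but the SAP describes them backwards: a low Emin after alprazolam would be read as marked agitation. If the scores carry the SAP coding, Emin and TEmin are taken from the wrong extreme, and changing the sign of the result afterwards does not recover peak relaxation. Protocol section 11.1 says VAS scores arrive in an external vendor file, and neither document states which coding that file carries.

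**Working it through.** **1. The two tables side by side**

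| | Protocol Table 5 | SAP Table 4 |
|---|---|---|
| Score 0 | relaxed end | agitated end |
| Score 100 | agitated end | relaxed end |
| Endpoints | Emin, TEmin, TA_AOE | Emin, TEmin, TA_AOE |
| What Emin measures | peak relaxation | peak agitation |

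Both cells are complete and unredacted. The midpoint wording is reordered along with the ends, so misreading of the PDF is an unlikely explanation.

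**2. What a reversal does to the endpoints**

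Let p be the score in the protocol direction and s = 100 - p the score in the SAP direction. Then:

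- Emin: min(s) = 100 - max(p)
- TEmin: the time of min(s) is the time of max(p)
- Area, if it is predose minus postdose: s(0) - s(t) = -(p(0) - p(t)), so the sign changes and the size does not

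The TA_AOE formula is not visible in the documents, so the last line is conditional on that definition.

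**3. One illustration (assumed profile, not trial data)**

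The inputs are predose plus the 13 scheduled treatment-phase postdose times, with an invented sedative-like response in the protocol direction:

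- Times (h): 0, 0.5, 1, 1.5, 2, 2.5, 3, 4, 5, 6, 7, 8, 10, 24
- Scores: 50, 42, 30, 22, 20, 22, 25, 30, 36, 40, 44, 47, 50, 55

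Protocol direction: Emin = 20 at 2 h. The trapezoid area of (50 - p) is 130.25 from 0 to 10 h and 14 × (0 - 5)/2 = -35 from 10 to 24 h. The time average is 95.25/24 = 3.97.

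SAP direction: Emin = 100 - 55 = 45 at 24 h, and the time-averaged area is -3.97. Peak relaxation is now an Emax of 100 - 20 = 80, which is not an endpoint.

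Against a placebo flat at 50, the Emin contrast is 20 - 50 = -30 in the protocol direction and 45 - 50 = -5 in the SAP direction. If the 24 h score were 50 instead of 55, the SAP-direction contrast would be 0. The algebra fixes which extreme is selected, but the size depends on the assumed profile.

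**4. Which coding is likelier**

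- The endpoints for the scale are minimum-effect endpoints in both documents.
- The parallel Drowsiness/Alertness scale has its sedative end at 0 in both documents ("0: Very drowsy 50: Neither drowsy nor alert 100: Very alert") and uses the same three endpoints.
- The SAP says it is based on protocol version 3.0.
- Protocol section 12.2 commits the study to being run according to the approved protocol.

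All four point to the protocol coding and a slip in the SAP.

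**5. Reach**

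SAP section 7.4.3 contrasts non-key secondary endpoints with two-sided intervals. The lists of GE-IR contrasts are blacked out. Assuming one per dose, Emin enters 1 (alprazolam vs placebo) + 3 (alprazolam vs GE-IR) + 3 (GE-IR vs placebo) = 7 contrasts. TEmin is only described (SAP section 7.4).

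**The case against.** The strongest reply is that an analysis plan does not alter the scale shown to subjects. Protocol Table 5 sets the anchors, protocol section 12.2 binds the conduct of the study to the protocol, and the SAP keeps both the scale name with relaxation first and the minimum-effect endpoints. On that view nothing in the analysis is wrong, and one descriptive row needs correcting.

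Most of this stands, and it is why the protocol coding is treated as likely. It does not remove the point. SAP Table 4 is presented as the scoring rule, and output interpreted from it would be read in the wrong direction. The documents also leave the coding of the vendor file unstated.

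Three stronger readings are tempting and are not supported:

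- A reader might infer that the trial data are reversed or the results wrong. No passage shows that the scale was given, or the scores stored, in the SAP direction.
- A reader might infer a second unlisted change from the Take Drug Again row of SAP Table 4, whose anchors also differ from the protocol's. In the text as read, the anchor cells of the unipolar rows just below are blank, and section 7.1.1 itself assigns those words to unipolar scales. The likelier explanation is a merged cell displaced in extraction, so that row is not evidence here.
- A reader might want a figure for the attenuation of the Emin contrast under SAP coding. Any such figure rests on an assumed time course: in the illustration, moving the 24 h score by 5 points moves the contrast from 0 to -5.

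**Conclusion.** The SAP Table 4 row is wrong as written: it contradicts the protocol and does not fit the endpoints the SAP itself retains. The contradiction is certain from the text. That it is a slip in the SAP is an inference, though a well-supported one.

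In the likely case there is no numerical effect; the harm is that relaxation would be described as agitation. In the unlikely case, Emin and TEmin for this scale would measure agitation, and a signed TA_AOE would reverse sign. No effect size is claimed for that case.

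Either way the consequence is minor. It concerns one non-key secondary scale. The primary endpoint, the key secondary endpoints, the validity test, the analysis populations and the sample size are unaffected, and other measures in the plan still cover sedation.

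**What to change.** Before unblinding, check the anchors programmed in the computerized scale and the direction of the scores in the vendor file.

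- If they match the protocol, correct the SAP Table 4 row to "0: Very relaxed 50: Neither relaxed nor agitated 100: Very agitated".
- If the scale was given in the SAP direction, reverse-score it (100 minus score) before deriving Emin, TEmin and TA_AOE, so that the endpoints keep the protocol's meaning, and record this in SAP section 12.

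The cost is one specification check and one corrected table row or, in the second case, one derivation line and one section 12 entry. No endpoint changes.
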